### 2.2 Secondary Objectives

# 2.2.1 Key Secondary Objectives

The secondary objective is to determine the rate of clinician-noted inaccuracies or major omissions in postoperative ML report cards.

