# 4.3.1 ML Report Card

The core intervention is the ML report card containing predictors of adverse events. Figure 4 is an example of the printed report card on a simulated patient. No personally identifiable information is included, other than a randomized study ID. The report card includes the operating room and date, to allow providers to know that it is for the current patient. Because the printouts are only created in operating rooms and PACU, this is sufficient information to place it in the correct chart. However, at other times the report card itself does not contain sufficient information for anyone without the studyID-patientID mapping file or pre-exising access to the EHR to determine the patient. Operating room number and time is included, but these can not be mapped to patients without the detailed surgical schedule in the EHR. The QR

code study links to an anonymous survey (no patient or provider information) for problems with the report card for the education and testing phase. The evaluation phase survey includes the additional questions in the appendix (triggered on date.

The ML risk profile generated for each patient will include risk of 30 day mortality, pulmonary complications and respiratory failure, acute kidney failure, transfusion, deep venous thrombosis, cardiac complications, and unplanned ICU admission. Additional predicted outcomes may be added based on feedback from healthcare team members. Risk profiles will display the average for all patients undergoing the same surgery, the risks calculated using preoperative assessments only (i.e. excluding intraoperative data), and the end-of-case values (i.e. including preoperative and intraoperative data). Literature-based estimates of probability of postoperative nausea and vomiting and severe postoperative pain will also be included where elevated. Expert-curated summaries of important variables will be included in the Epic report card, which include: estimated blood loss, fluids given, opioids given, duration of anesthesia, antibiotics given. Explanatory tools for the risk profile will also be generated based on SHAP values [Lundberg 2017] identifying the variables with greatest influence on predictions

Figure 4: Example ML report card

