#### 4.4 Outcomes

# **4.4.1 Primary Outcome Measures**

The primary outcome will be self-reported handoff effectiveness.

The following survey questions will be asked of postoperative providers:

Did you receive at handoff all the information you needed to safely take care of this patient?

[Yes, No]

Did you receive information from the team giving handoff to explicitly help you manage any potential complications or problems? [Yes, No]

If so, please list what problems / topics were discussed? [Free response]

[If with-intervention phase \* ] Did you look at or discuss the postoperative report card for this patient? [Yes, No]

[If  $^*$  yes] Did the report card contain any information that was notably misleading or incorrect?

[Yes, No]

[If yes, please describe: text box]

[If \* yes] Are there any important pieces of information that the computer should have included in the report card but didn't?

[Yes, No]

[If yes, please describe: text box]

[If \* yes] How much did the ML report change questions asked or information transfer at handoff?

[ Not applicable , Not at all , a little , a fair amount , a great amount ]

[If \* yes] How much effort was accessing the report card? [Very easy, easy, some effort, hard, unable to get to it or had to ask for help]

[If \* yes] Was the information presentation in the report card easy to understand? [Easy, some effort, hard to understand, unable to use or had to ask for help]

[If \* yes] Was the information in the report card relevant?
[a great amount, a fair amount, modestly, mostly not, not at all, not sure]

[If \* yes] Was the information in the report card useful to decision making or helpful to your understanding of the patient?
[a great amount, a fair amount, modestly, mostly not, not at all, not sure]

The following questions will additionally be asked of PACU resident physicians:

Did you participate in handoff for this patient? [Yes, No]

Did you visit this patient's bedside or speak to their nurse before being asked to sign them out? [Yes, No]

Figure 7 illustrates the RedCAP survey for safety questions which will be included throughout the study.

Figure 7: RedCAP Safety Survey

Postoperative Al Risk Report Card	Resize font:  Returning?

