This form is to collect reports of problems with the Al generated risk estimat study PI at [contact] if this doesn't cover your needs. The for does try to link to a patient so that we can figure out what caused the proble appreciate all feedback. The study team will never try to figure out who subn you.	rm doesn't track who you are (it is anonymous) but it em. This is an experiment (IRB: 202103210) and we
This form is to report safety problems with the Al postoperative risk report it does try to link to a patient so that we can determine what happens is approved for HIPAA-protected information.	
This field should auto-populate with a study ID from the link you followed to get here. Otherwise, (1) if you have a QR code with the email me link, and you are at a machine with a barcode scanner, click in the below field and scan the QR code (2) this is a HIPAA-protected portal, you can enter any of the Epic patient IDs and the study team will link it to the correct person.  * must provide value	d46e6e6bb147f7ebdf645e2e9be156172c32897e  Expand
Common problems:	☐ The report card is for the wrong patient ☐ The report card generated on a non-surgical patient ☐ The report card generated too early (preop) ☐ The report card generated too late (not immediately postop) ☐ The risk estimates are too low ☐ The risk estimates are too high ☐ The risk estimates were otherwise confusing ☐ The report card does have / use data that I think it should ☐ The report card has incorrect data ☐ The report card display / formatting was broken
This problem made the report card unsafe  * must provide value	○ Yes ○ No reset
Tell us anything about the problem	
	Expand
If you have comments or suggestions that aren't a problem w	vith the report card, include them here

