### 4.4.2 Secondary Outcome Measures

A research assistant will directly observe up to 150 OR - PACU and PACU-Ward handoffs in the intervention phase. An assessment form is attached. After direct observation, the research assistant may ask unstructured clarifying questions and present the survey questions discussed above.

We will conduct 20-30 debriefing interviews with ward and PACU clinicians on their perception of handoff effectiveness and the usefulness of the report card. These will be audio recorded and transcribed.

We will extract exploratory clinical outcomes from the EHR: ICU admission, hospital length of stay, discharge disposition (including death), and changes in serum creatinine (acute kidney injury).

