- 3) Because of the need to link intraoperative risk models to patient locations and outcomes, it is not possible to conduct it without identifiable private information.
- 4) The waiver will not affect the rights or welfare of the participants. As the Secretary's Advisory Committee on Human Research Protections notes in 2008, this requirement related to any other legal consent requirements, which are not present in this case. Additionally, we should consider if the population would object to the waiver if informed of it or believe that it could cause them harm. We believe that due to the novel nature of the technology, standard-of-care control arm, minimal risk, and diversity of successful PACU staffing models participants would not object to participation.
- 5) There are no special circumstances necessitating post-facto information provision to the patient. This requirement is intended for research involving deception.

A participation document will be included at the beginning of the workday for PACU physicians and postoperative providers receiving messages describing the study.

A partial waiver of informed consent for providers is requested. Providers are exposed to the report card and may optionally complete the above survey reporting inaccurate data. Because (1) surveys do not collect identifying information and participation requires active effort, (2) predicting the applicable providers is impossible, separate consent forms will not be obtained and we request a waiver of consent. Study information is included in the survey link which includes that their participation is completely voluntary, that no communication is made to the institutional leadership, and that all stored information is anonymized to the extent possible.

- 1) The study presents non-significant risk to participants. Survey responses are securely stored and contain no identifying information. Providers can skip the survey without any harm
- 2) The project is not scientifically feasible without a waiver of consent. Because the midlevel and nursing providers for this subset of patients are not knowable ahead of time, we would need to consent every possible nurse and midlevel provider.
- 3) No identifiable private information is requested.
- 4) There is no foreseeable effect on the rights or welfare of the participants. Because it is unidentified, there is no mechanism for (non) participation to affect the providers.

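### The card-delivered evaluation survey is voluntary and appears to be built on the problem-report form, so the inaccuracy rate among responders cannot be taken as the rate among cards issued

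*Combined protocol and SAP*

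**What the plan says.** Section 2.2.1 sets out to "determine the rate of clinician-noted inaccuracies or major omissions in postoperative ML report cards", and section 1 treats this rate as the measure of the card's safety.

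On the instrument, section 4.3.1 says the QR code "links to an anonymous survey (no patient or provider information) for problems with the report card for the education and testing phase". Its next sentence moves to the evaluation phase: "The evaluation phase survey includes the additional questions in the appendix", switched on by date. Section 4.4.1 adds: "Figure 7 illustrates the RedCAP survey for safety questions which will be included throughout the study". The form in Figure 7 announces its purpose at the top ("This form is to report safety problems with the" AI risk report). It offers a checklist of common problems and has a compulsory yes/no item on whether the problem made the card unsafe. Section 7.3 says: "Providers are exposed to the report card and may optionally complete the above survey reporting inaccurate data". It adds that providers may skip the survey.

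There is a second route. Under section 4.4.2 a research assistant observes up to 150 handoffs in the intervention phase, after which "the research assistant may ask unstructured clarifying questions and present the survey questions discussed above".

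Section 4.5 gives a 95% upper limit of 2.4% if none of 150 reports is rated inaccurate. Section 5.3 covers the comparison of acceptable handoffs and an exploratory per-protocol analysis. It gives no denominator, response proportion or non-response rule for the inaccuracy rate.

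**The concern.** A form that opens by asking for problems, and that requires an answer about how unsafe the problem was, suits a provider who has found a fault. A provider with nothing to report meets a compulsory question that does not apply. If the evaluation questions sit on that form, and completion is voluntary, the chance of a response may depend on the answer being measured.

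Two simple summaries then go wrong. If fault-finders respond more often, faults divided by responders is too high. Faults divided by cards issued is too low whenever some fault-finders stay silent. If answers obtained in person are added without a label, the result also depends on how many came by each route. What is at stake is the rate on which the plan rests its judgement of the card's safety.

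**Working it through.** **Inputs from the documents.** Section 4.5: 0 of 150, upper limit 2.4%. Section 4.2.2: 350 evaluation patients, with 60 of 90 days with intervention. **Assumed.** Patient volume is even across days, so cards issued are about 350 × 60/90 = 233. The response ratio *k* (response probability after finding a fault, divided by that after finding none) is not given; 0.5 to 5 is used. Every card is treated as read.

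**1. The plan's own figure.** The exact two-sided 95% upper limit for 0 of *n* is 1 − 0.025^(1/*n*). For *n* = 150 it is 2.43%, so the 2.4% is reproduced. It describes issued cards only if the 150 are all the cards, or a sample in which response does not depend on finding a fault (*k* = 1).

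**2. Rate among responders.** With true rate *p* per card, the rate among responders is *q* = *kp*/(*kp* + 1 − *p*). For *p* = 5%:

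| *k* | *q* |
|---|---|
| 0.5 | 0.025/0.975 = 2.6% |
| 1 | 5.0% |
| 2 | 0.10/1.05 = 9.5% |
| 3 | 0.15/1.10 = 13.6% |
| 5 | 0.25/1.20 = 20.8% |

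**3. The same in counts.** Take 233 cards, *p* = 5%, and response of 60% with a fault and 20% without (*k* = 3). Faulty cards: 11.65, giving 11.65 × 0.6 = 7.0 responses. Sound cards: 221.35, giving 221.35 × 0.2 = 44.3. Faults are 7.0/51.3 = 13.6% of responders and 7.0/233 = 3.0% of cards. The true 5% lies between the two.

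**4. What happens to the limit.** Inverting, *p* = *q*/(*q* + *k*(1 − *q*)). A limit of 2.43% among responders corresponds, among cards, to 4.7% (*k* = 0.5), 1.2% (*k* = 2), 0.8% (*k* = 3) or 0.5% (*k* = 5). The stated limit is therefore conservative when *k* > 1 and too low only when *k* < 1.

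**5. With no assumption on *k*.** If 150 of 233 cards are answered and none is faulted, the faulty share of issued cards lies between 0/233 = 0% and (233 − 150)/233 = 35.6%.

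**The case against.** The strongest reply is that the evaluation survey is not simply a fault report. The specimen card in Figure 4 invites every recipient to take the survey and asks for feedback in general terms. Section 4.4.1 lists two neutral handoff questions first, and puts the fault items only to providers who had seen or talked about the card. The sentence about problems with the card refers, in its own words, to the education and testing phase. The evaluation form is not shown, so its header and layout cannot be checked. The card's QR code also cannot be the only route: outcomes are assessed on days when no card exists, and the research assistant may put the questions in person.

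Much of this stands. A reader might infer that the evaluation survey *is* the problem form. The documents support only that it appears to be built on it: questions are added, and the safety form runs throughout. A reader might also infer that the rate will be overstated. That is the likelier direction, but no response rate or ratio is given, and a fault-finder might equally set the card aside without answering. Finally, a reader might infer that the 2.4% limit is useless. Under over-reporting the opposite holds (step 4).

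The reply leaves the gap open. A neutral invitation does not make a voluntary response independent of its content. The in-person route is optional and needs consent (section 7.3). Days without a card contribute nothing to this rate. The plan records neither the route nor the response proportion.

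**Conclusion.** The concern holds in a limited form. The card-delivered survey is voluntary and, as described, appears to carry the problem header and the compulsory item on safety. The inaccuracy rate among responders therefore cannot be assumed to equal the rate among cards issued, and the plan collects nothing that would show how far apart they are.

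The size is illustrative only: a 5% card rate could appear as anything from 2.6% to 20.8% for *k* from 0.5 to 5, and those ratios are assumptions. The 2.4% limit is arithmetically right. It fails as a bound on issued cards only if fault-finders respond less often than others. This affects a descriptive secondary rate in a pilot. It is worth correcting because that rate is the study's safety figure and the correction is cheap.

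**What to change.** - **Sections 4.3.1 and 4.4.1:** give the evaluation survey a neutral header. Move the Figure 7 checklist and its compulsory item on safety to a separate link for reporting a problem.
- **Route:** record for each response whether the research assistant presented it or the provider completed it from the QR code or Epic link.
- **Section 5.3:** use the study ID to report the share of issued cards with any response. Report the inaccuracy rate separately by route, taking the research-assistant responses as the less selected estimate. Give problem-link submissions as a count over all cards issued. State how answers from several providers on one card are combined.
- **Section 4.5:** state which responses form the 150.

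Restricting the rate to solicited responses would not serve, because the printed card already solicits everyone.

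The cost is a header change, a second link, one data field and a few sentences of analysis plan. Each route's rate rests on fewer responses: if the 150 split evenly, 0 of 75 has an upper limit of 1 − 0.025^(1/75) = 4.8% instead of 2.4%. The in-person route also keeps its own selection through consent, so neither rate should be presented as free of bias.

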#### Please place this with the preop/pacu signout sheet

#### Generated at 06/20/2022, 12:11:07 PM for Room: BJH OR POD 3 ROOM 302

This is an experimental (IRB: 202103210) integration of AI to identify high risk postop patients. This does not replace usual handoff, but if risks below are high, it may be worth adding the plan and assessment to your handoff. Many factors are not included in the prediction models; always use your clinical judgement. With concerns or questions please contact [contact]. Please use the QR code to take an anonymous survey (no PHI, phone is ok). For BJH computers with a scanners, open chrome, click the address bar, and scan; some scanners add a leading and trailing slash. We really feedback to make it work better! I can also be reached at [contact].

#### Postoperative risk report

Outcome	Outcome	Risk	Surgery	Average
	% for	percentile	rate	outcome
	patient			rate
death_in_30	0.8	76	0.9	1.8
pulm	0.1	70	0.1	0.3
transfusion	6.8	69	20.8	11.5
DVT_PE	0.5	67	2.4	0.9
cardiac	1.3	66	5.5	2.6
ICU	4.8	63	24.3	15.2
post_dialysis	0.0	60	1.4	2.4
long_vent	1.0	55	4.4	6.0

on the words contained in the scheduled surgery, Average outcome = all inpatient postop at BJC. Outcome definitions: Cardiac = new diagnosis of CHF or MI, elevated troponin or BNP, new A Fib. Pulm = pneumonia, reintubation in 5 days. postop\_dialysis = new dialysis. DVT\_PE = diagnosis of DVT or PE. Transfusion = transfusion > than 1 unit of any product. ICU = ICU in

"Surgery rate" = prediction based

first 7 days. death\_in\_30 = death in 30 days.

Table 1: Largest contributors to overall adverse events

Variable	Value	relative
		import
Deep Venuous	0.0	1
ThrombosisMissing		
Diabetes	0.0	0.88
MellitusMissing		
Partial Thromboplastin	29.0	0.63
Time		
Pulmonary	0.0	0.63
Hypertension		
Obstructive Sleep Apnea	0.0	0.54
Alkaline Phosphatase	416.0	0.49
Weight	70.8	0.29
PreOp Systolic	NA	0.25

#### Methods note

Risks generated using pre-anesthesia assessment, major comorbidities, laboratory values, and preoperative vital signs; errors in these values can significantly affect the calculations. Risk calculations use gradient boosted decision trees trained on BJH inpatient data 2019-2021. see https://pubmed.ncbi.nlm.nih.gov/31558311/

study ID 86915c307cbd5e01531052a04ff901d94371e8bf

The ACT detects that cases are near completion and that a report card should be triggered in two ways. First, the circulating nurse in each room electronically marks that a room is "close" in the EHR, usually during closure, to ensure that subsequent patients are called to the preoperative area and supplies for the next case are readied. This is performed with high fidelity as it is considered important to prevent case delays. The displayed OR schedule in Epic changes color, making this easily recognized. Second, an algorithm detects when changes in the anesthesia record suggest that the case is concluding. Both of these features cause the ML dashboard in the ACT (Figure 5) to highlight the patient as needing review to validate the report card. After manual validation, the report card will print directly in the operating room and a notification is sent to the circulating nurse to add it to the chart and provide it to the anesthesia team for handoff. The risk profile is then made active in a Best Practice Advisory in Epic.

-	nesthesia Control Tower ML Dash eview." Additional columns not sho			formation reda	acted. Yello	w highli	ght implies
Room Name	Description	akigr1\$	cardiac \$	death_in_3d=	DVT_PE\$	ICU \$	post_dialysis
BJH OR POD 2 ROOM 209	###LAPAROSCOPIC CHOLECYSTECTOMY	2.90%	1.60%	0.10%	8.80%	5.20%	0.10%
BJH OR POD 3 ROOM 301	EXPLORATION LIVER TRANSPLANT WITH WASHOUT LIVER BIOPSY AND BILE DUCT REVISION	67.10%	6.90%	7.60%	1.20%	93.40%	0.90%
BJH OR POD 2 ROOM 211	TRACHEOSTOMY PERCUTANEOUS	40.30%	2.70%	3.50%	7.40%	94.50%	0.20%

Communicating from the ACT to the PACU physicians presents several advantages. First, the ACT clinician is familiar with the general model of ML output generated by AlertWatch and will filter out obvious errors from reaching the care team and potentially harming the patient, minimizing risk to participants. Second, because on a given day a single attending physician and resident oversees the PACU at BJH South Campus, friction related to communication between the ACT and these providers will be minimized as these contacts become routine. Both parties will have the opportunity to rapidly adjust to the presence of the report card as they will process multiple such reports per day. Third, because the ACT-postop communication happens before formal handoff, it will allow these providers to look into higher risk cases before they arrive and ask more detailed questions during handoff. We anticipate that most interactions will consist of simply forwarding the report card. The ACT will not communicate directly to PACU nurses or ward providers.

ML output will be generated on a server controlled by the investigators and administered by Washington University Information Technology. This is the same server and data access mechanism used by the ACT team. A feed of preoperative and intraoperative data extracted from the Epic EHR designed for use in the AlertWatch system is currently saved in a database maintained by BJH and exposed for authorized users to access, which we will access using encrypted transport mechanisms. The server will also have a TLS-encrypted and password protected web interface (dashboard) for debugging, message generation, and manual end-ofcase triggering. The web interface will allow study technical staff and ACT clinicians to look up current and previous risk profiles by study identifier, patient identifier and date, or date, time, and operating room number. It will also allow them to manually enter that a case is concluding, and to mark a day as "with-intervention". The study identifiers, date, time, end of case marker, intervention indicator, and ML output will be stored on the WUSTL Research Infrastructure Services Data Storage Platform. The RIS Data Storage Platform is a scalable distributed storage solution with an integrated long-term archive. It is institutionally approved for protected health information, and requires WUSTL-key authentication and 2-factor authentication outside WUSTL facilities. Data access is granted only on a per-user basis and logged. The ML server is behind the Washington University firewall and inaccessible from off-campus computers.

To avoid misleading postoperative providers, we will create a brief educational sheet explaining the purpose of the study and the items included in the risk profile (attached). The educational sheet will include the calibration accuracy and other appropriate metrics regarding the predictions. For example, at the screening threshold we will use the sensitivity for AKI is about 50%, meaning that the provider should not be falsely reassured by not receiving an alert. We will stress that these risk predictions were formed in the context of usual care at BJH, and that a

lower risk prediction does not justify withholding a therapy that they would otherwise give. These sheets will be linked in the report card. A draft of the sheet is included with this application, but it may be modified based on feedback from providers. We also plan to periodically recalibrate the ML algorithms based on new data, and will update the accuracy metrics accordingly.

